4.1.11. Dose Reduction

To potentially reduce drop-out rates from AEs or tolerability issues during the study, the treating physician may choose to reduce the dose of study product by 1 capsule per day on a temporary or permanent basis. The impact of any temporary or permanent reduction in dose > 30 days will be assessed in sensitivity analyses of the primary and first secondary efficacy outcomes.

4.1.12. Discontinuation from Study Product but Continuation in Study

A subject may discontinue study product and continue in the study. If a subject permanently discontinues study product, they will be asked to continue in the study for efficacy and safety follow-up with Visits 5 and 8 performed off study product, starting with the next one of these visits that occurs after discontinuation of study product. For subjects who do not withdraw consent and agree to return for these visits, an additional 28-day safety follow-up after Visit 8 will not be done. Safety and efficacy data will be collected during these visits and included in analyses of safety and efficacy data. The impact of having these subjects remain in the study will be assessed in sensitivity analyses of the primary and first secondary efficacy outcomes.

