4.1.2. Schedule of Visits and Assessments

Schedule of clinical assessments/procedures for all subjects is presented in [Appendix 2](#). Additional assessments/procedures for France are presented in [Appendix 4](#).

The following will be assessed at all in-person visits:

- Endpoints related to PEx, CRISS, spirometry
- Concomitant medications
- Adverse events
- Study product tolerability
- Vital signs (systolic and diastolic blood pressure, pulse rate, respiratory rate, body temperature, height and weight)
- Brief Physical examination

- Contraceptive assessment and pregnancy screening for women of childbearing potential
- Complete blood count with cell differential and platelets; metabolic panel; and urine dipstick

Other assessments will be done less frequently:

- 12-lead ECGs including QT/QTc intervals (Visit 1, Visit 5, and Visit 8)
- CFQ-R questionnaire (Visit 1, Visit 5, and Visit 8)
- CRP and ESR (Visit 1, Visit 2, Visit 5, and Visit 8)
- Plasma concentrations of lenabasum and its metabolites (Visit 1, Visit 2, Visit 5, and Visit 8). Plasma concentrations and metabolites of lenabasum and ARCI-49 questionnaire will be assessed on Visit 1 before and 3.0 ± 0.5 hours after dosing.

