6.4.3. Safety Population

The safety population will consist of all subjects who received any study product. Analyses performed on the safety population will be per the study product received.

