9.2. Discontinuations, Lost to Follow-up, and Unscheduled Visits

All assessments of efficacy and safety done after discontinuation of study drug will be included in primary efficacy and safety analyses, for subjects who permanently discontinue study product, do not withdraw consent, and continue in the study.

If a subject withdraws consent, their last regularly scheduled study visit before withdrawing consent will be their last visit for efficacy and safety assessments.

If a subject is lost to follow-up, their last regularly scheduled study visit that they attended will be considered their last visit.

Efficacy assessments done at Unscheduled Visits and Possible PEx visits will be counted in efficacy analyses, only if AUQ-R at that visit indicates that the subject is having a PEx that meets primary or secondary definitions of a new PEx. Otherwise, efficacy assessments done at unscheduled visits and Possible PEx visits will be included only in listings.

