11.1. Adverse Events

Throughout the duration of the study, the investigator or designees will closely monitor each subject. All AEs which occur during the study, whether observed by the investigator or by the subject, and whether or not thought to be related to study drug will be recorded. The description of the AEs as recorded on the eCRF will include a description of event, start date, stopping date, intensity, if it was serious, relationship to study drug, what actions were taken with respect to the study drug, if treatment was required and the subject's outcome.

The investigator must evaluate each AE for its relationship to the study drug and for its seriousness. All AEs related to study drug must be followed until resolution or until they become stable.

AEs will be coded using Medical Dictionary for Regulatory Activities, Version 22.1.

Treatment-emergent AEs include all AEs onset between first dose and last dose of the study product, inclusive. TEAEs and AE onset during the 28-day follow-up will be summarized separately. Any AEs that occur before first dosing will be summarized in a table as Pre-Treatment AEs.

An overall summary by treatment cohort will be presented that includes the number and percentage of subjects who experienced at least one TEAE, serious TEAE, TEAEs by maximum severity, TEAEs by strongest relationship to study product, TEAEs leading to study product withdrawal, TEAE of dizziness ([Section 11.2](#)), and death. The total number of TEAEs will also be presented. The overall summary of TEAEs will also be presented by age group (< 18 years and \geq 18 years).

The number and percentages of subjects with the TEAEs listed below will be summarized by SOC, preferred term, and treatment separately. The TEAEs listed below will also be summarized by age group (< 18 years and \geq 18 years). If a subject reports the same preferred term multiple times within the same SOC, that subject will only be counted once for the SOC. As with the preferred term, if a subject reports multiple conditions within the same preferred term, that subject will only be counted once for the preferred term.

- TEAEs
- Serious TEAEs
- TEAEs leading to study product withdrawal
- TEAEs of dizziness (AE of special interest)
- TEAEs by maximum severity
- TEAEs by strongest relationship to study product
- TEAEs in \geq 2% of subjects in lenabasum 20 mg BID cohort
- TEAEs of abuse potential; relevant preferred terms include the following:

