11.3. Clinical Laboratory Tests

For serum chemistry and hematology, the results for each parameter in the International System of Units will be summarized by treatment and visit using continuous summaries. Change from baseline and shift tables will also be provided comparing post-baseline visits with baseline.

For urine dipstick tests, the results for each parameter will be summarized by treatment at each visit using number of subjects and percentages for each result category.

Serum and urine pregnancy test results will be provided in a data listing only.

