11.6. Twelve-Lead Electrocardiogram

[figure not shown]
Electrocardiogram (ECG) parameters include heart rate, RR interval, QRS duration, PR interval, QT interval, QT interval correction by Fridericia's formula, and if needed by Bazett's formula. In addition, ECG evaluation of abnormality and interpretive statements will also be reported.

The actual values and change from baseline for every post-baseline visit/time point in each ECG parameter will be summarized by treatment and visit/time point.

Electrocardiogram evaluation of abnormality (normal versus abnormal) will be summarized by treatment and visit/time point using number and percentage of subjects in each result category.

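### Laboratory, vital-sign and ECG values taken off study product at Visits 5 and 8 are pooled into the by-treatment safety tables with no on-product limit

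*SAP*

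**What the plan says.** On permanent discontinuation of product, Section 4.1.12 states that subjects stay under follow-up: "they will be asked to continue in the study for efficacy and safety follow-up with Visits 5 and 8 performed off study product". It continues: "Safety and efficacy data will be collected during these visits and included in analyses of safety and efficacy data". Section 9.2 gives the same rule for analysis: "All assessments of efficacy and safety done after discontinuation of study drug will be included in primary efficacy and safety analyses". It applies to subjects who stop product, keep their consent and remain in the study.

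The treatment label comes from Section 6.4.3: "Analyses performed on the safety population will be per the study product received". That label belongs to the subject and does not change when the subject stops taking product.

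The by-visit sections use this label. For chemistry and haematology, Section 11.3 says "the results for each parameter in the International System of Units will be summarized by treatment and visit using continuous summaries", with change-from-baseline and shift tables in addition. Section 11.4 treats vital signs in the same way. Section 11.6 says "The actual values and change from baseline for every post-baseline visit/time point in each ECG parameter will be summarized by treatment and visit/time point", and adds a normal/abnormal count by visit. Section 4.1.2 schedules ECGs at Visits 1, 5 and 8 only.

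Adverse events follow a different rule in Section 11.1: "Treatment-emergent AEs include all AEs onset between first dose and last dose of the study product, inclusive". Section 13 describes the efficacy and safety analyses as in general on-treatment, with a period that runs to Week 28 and is cut short only when a subject leaves the study.

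**The concern.** A by-visit safety table headed with a lenabasum dose is normally read as showing subjects who are taking that dose. Under these rules the Visit 5 and Visit 8 rows mix values on product with values from subjects who stopped weeks or months before. If a drug effect on a laboratory test, pulse or ECG interval reverses after stopping, the later values move the cohort mean and the shift counts back towards baseline. Placebo subjects have no drug effect to lose, so the contrast with placebo shrinks.

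The SAP is also not consistent with itself. It confines adverse events to dosing time but sets no such limit for measured safety values and gives no reason for the difference. Section 4.1.12 plans sensitivity analyses on the retention of these subjects for two efficacy outcomes and none for safety.

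**Working it through.** No figure in the SAP can be reproduced for this point, so the check has two parts: do the rules let these values in, and how large could the effect be?

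**1. Do the values enter the tables?**

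- Collected: yes, at Visits 5 and 8 (Section 4.1.12).
- Included in the safety analyses: yes (Sections 4.1.12 and 9.2).
- Removed as unscheduled: no. Section 11 sends only unscheduled and PEx visits to listings, and Visits 5 and 8 are scheduled.
- Removed by a last-dose rule: no. Sections 11.3, 11.4 and 11.6 contain none. The last-dose limit in Section 11.1 concerns adverse events only.
- Removed by Section 13: no. Its period ends early at study discontinuation. A subject who stops product and stays in the study is still inside it.

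**2. Which rows are affected?** Off-product subjects are asked back for Visits 5 and 8 only. For laboratory tests and vital signs, the rows for the other on-treatment visits keep their on-product content. For ECG, both scheduled post-baseline visits are affected.

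**3. How long after the last dose?** Visit 5 falls at Week 16 and Visit 8 at Week 28.

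- Stopped just after Visit 1: about 16 weeks at Visit 5 and about 28 weeks at Visit 8, since both visits are attended.
- Stopped just after Visit 5: 28 − 16 = 12 weeks at Visit 8.

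**4. How large is the dilution of a mean?** Let f be the share of a cohort's values at a visit that are off product, and d the mean shift among on-product subjects. If the effect has fully reversed in the others, the pooled mean shift is (1 − f) × d + f × 0 = (1 − f) × d. The SAP does not give f, so it is an assumption here. The counts suppose that all randomised subjects supply a value.

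| Assumed f | 20 mg (n = 166) | 5 mg (n = 83) | Share of d shown | A 5-unit shift shows as |
|---|---|---|---|---|
| 2% | about 3 | about 2 | 98% | 4.90 |
| 5% | about 8 | about 4 | 95% | 4.75 |
| 10% | about 17 | about 8 | 90% | 4.50 |
| 15% | about 25 | about 12 | 85% | 4.25 |

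**5. What if those who stop are the ones who react?** Suppose that 10% of a cohort would be abnormal if all stayed on product, and that 2% of off-product values are abnormal (both assumed).

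- Stopping unrelated to reaction, f = 5%: pooled rate 0.95 × 10% + 0.05 × 2% = 9.6%.
- All who stop are reactors, f = 5%: pooled rate (10% − 5%) + 0.05 × 2% = 5.1%.
- Same case, table limited to on-product subjects: 5% / 95% = 5.3%.

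The last two lines show that dropping off-product values makes a table describe what its heading says, but does not bring back the reactions of those who stopped.

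**The case against.** Several points on the other side stand.

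- The tables are descriptive and no safety tests are planned, so no error rate is touched.
- The primary safety endpoint is TEAEs, which are confined to dosing time. Serious TEAEs and TEAEs leading to withdrawal of product are tabulated by cohort, and all data are listed by subject and visit. Much of the harm in subjects who stop would be seen there.
- Keeping all scheduled visits under the product received is a deliberate choice, and collecting the off-product data is good practice.
- Section 13 can be read as intending an on-treatment basis. That makes the matter partly a conflict between sections, although Section 13's own definition does not exclude these values.
- Some SAP text is not in the public copy (Section 11.7, for instance, refers to a Section 4.3.3 that is not shown). The absence of a limit is established for the visible text only.

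A reader might also infer more than the SAP supports:

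- *That the dilution is 15% because drop-out is planned at 15%.* That figure is for subjects who do not complete the study: 415 × 0.85 = 352.75, which matches the roughly 352 completers in Section 4.1.5. People who leave supply no later values and cannot dilute a visit. The relevant group stops product and stays, and its size is not given.
- *That all safety results are biased towards no harm.* TEAE tables and the other visits' laboratory and vital-sign rows are not affected, and an effect that persists after stopping is not diluted.
- *That a restriction to on-product values yields the true on-drug change in all subjects.* It does not, as the last step of the working shows.

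None of this removes the core point: the Visit 5 and 8 rows pool two different states under one heading.

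**Conclusion.** The point holds as a gap in how the measured safety data are displayed. Sections 4.1.12 and 9.2 bring off-product values into the safety analyses, and Sections 11.3, 11.4 and 11.6 set no on-product limit, in contrast to the TEAE rule in Section 11.1. Section 13's on-treatment wording does not close the gap.

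For reversible effects the direction is towards no difference from placebo. The size is unknown and may well be modest on average: a loss of 2% to 15% of a mean shift under an assumed off-product share of 2% to 15%, with complete reversal and stopping unrelated to response. It can be larger for rates of abnormal values if those who stop are those who reacted. ECG deserves most attention, because no other scheduled post-baseline visit gives an undiluted view. The repair should be made before unblinding.

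**What to change.** 1. Add an on/off-product flag to each laboratory, vital-sign and ECG record, derived from the last-dose date.
2. In Sections 11.3, 11.4 and 11.6, base the Visit 5 and Visit 8 summaries, changes from baseline, shift tables and normal/abnormal counts on values up to last dose plus a short window, its length fixed before unblinding.
3. Show later values in a separate off-product summary by cohort.
4. Reconcile Sections 4.1.12, 9.2 and 13, so that the inclusion rule and the on-treatment wording say the same thing about these values.
5. State that the restricted tables describe subjects still on product and are to be read with the tables of TEAEs leading to withdrawal.

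The cost is SAP wording, one derived flag, one extra table set, and slightly fewer subjects in the Visit 5 and Visit 8 rows. No data are discarded and visit conduct does not change. Section 2 rules out sponsor changes after signature but allows supplementary analyses identified in the CSR. If the SAP is already signed, the split display can be added by that route.

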4.1.13. Early Discontinuation from Study

Reasons for early discontinuation from the study include: death; AE; lack of efficacy - withdrawal by subject; lack of efficacy – physician decision; physician decision – other; withdrawal of consent by subject; lost to follow-up; non-compliance with study; pregnancy; study termination by sponsor; and other.

Subjects who withdraw consent will not have any efficacy or safety follow-up assessments following withdrawal of consent.

Participants who are discontinued permanently from study product due to an AE will be followed until resolution or stabilization of the event.

4.1.14. Coronavirus Disease 2019 (COVID-19)

Starting in winter 2019/2020, a pandemic of infection with new coronavirus (2019-nCOV) caused national and regional governments to restrict travel and gatherings of multiple people. Access of clinical study subjects to study sites and staff was severely restricted from mid-March 2020, as was access of study monitors to monitor study data at sites and remains restricted at the time of writing this SAP. At the time the restrictions began, all subjects had completed Visit 5 (Week 16) of the study.

The Sponsor developed and communicated a plan to manage safety and efficacy analyses of study subjects and maintain continuity of supply of study product to subjects, which is consistent with the *FDA Guidance on Conduct of Clinical Trials of Medical Products During COVID-19 Public Health Emergency (FDA COVID-19 Conduct Guidance, March 2020)*. This plan was communicated internally first and then to sites during a series of webcasts on March 12 and 13, 2020, just before most restrictions began to take effect. As the Sponsor's management of the impact of COVID-19 evolved, any changes to the plan were communicated to the sites through e-mail or phone calls. The plan was communicated to internal study staff, vendor staff, study site staff, and the DMC. Details of the plan and communication are maintained separately at Corbus.

Approaches to mitigating potential major impact of COVID-19 on performance of study JBT101-CF-002 are summarized in **Table 1**.

Table 1. Summary of Mitigation of Negative Effects of COVID-19 on Study JBT101-CF-002

COVID-19 Negative Effects on Execution of study JBT101-CF-002	Mitigation

Subjects not able to have study visit at site because site is closed, site staff cannot travel, or subject is at high risk of traveling to site
 
• Missed visits• Visits outside study window• No safety assessments on site at Visit 5-8 or safety follow-up visit• Missed efficacy assessments at Visits 5-8• Subjects unable to get study product at site	
Extend visit windows by 1 week, to \pm 2 weeks, to increase opportunity for study visits at site and full study evaluation
 
Obtain safety follow-up including use of contraception using interview-based assessments over the phone or computer, between subjects and physicians. Document TEAEs and use of contraception per protocol
 
Obtain safety lab follow-up at local laboratories when possible. Results will be reviewed by study staff, put into source documents, but not study database
 
Obtain concomitant medication history using interview-based assessments over the phone or computer. Document concomitant medications per protocol
 
Obtain information of PEx using interview-based assessments over the phone or computer, between subjects and physicians. Document PEx per protocol
 
To maintain continuity of dosing with study product:
 
• Make provisions for sites to ship study product directly to subjects. Obtain a DEA waiver for lenabasum so US sites can ship study product directly to subjects• Allow subjects not to return unused study product to site until end of study and to use that study product if needed to maintain continuity of dosing• Maintain subjects on a reduced dose of study product if direct shipment of study product to subject will not arrive in time to allow subject to continue to take full dose of study product. This approach is preferred to continuing subject on full dose of study product, then temporarily discontinuing study product altogether while waiting for direct shipment of study product to subject to arrive

Study staff not on site or have restricted access to site to enter study data. 
• Late data entry• Incomplete data entry	Closely monitor site visits and data entry to determine what data will be late versus what will not be obtained. Work with sites to get data entered whenever possible
External monitors unable to travel to or enter study site to monitor data 
• 100% source document verification will not be possible	Remote data monitoring, as allowed by site/country policies. Perform and document oversite of remote data monitoring Central data monitoring when data cannot be verified on site or by remote monitoring. Perform and document oversite of central data monitoring Resume source document verification on site when travel restrictions and access allow

Treatment assignment does not influence the negative effects of COVID-19 on execution of study JBT101-CF-002 or the plans put into place to mitigate those effects. The COVID-19 pandemic is not expected to introduce bias into the statistical analyses of the data.

A Table listing amendments to study plans to ensure continuity and oversight of the study will be included in the JBT101-CF-002 CSR.

A listing by subject and a table summarizing COVID-19 associated events by treatment cohorts and combined lenabasum cohorts will be provided. This listing and table will include protocol deviations.

Protocol deviations related to COVID-19 are expected to fall mostly into categories of study visits outside of windows, missing efficacy assessments, and short periods of temporary reduction/discontinuation of study drug.

Safety oversight was maintained throughout either with onsite visits or with interview-based safety assessments by the treating physician.

The following effects of COVID-19 on subject disposition are identified before database lock:

- No subject early terminated before Visit 8 because of COVID-19
- All subjects had safety follow-up during COVID-19
- On March 16, 2020, when staff at Corbus began work-from-home policy for COVID-19, 18 subjects (~4%) had not yet completed Visit 6 (Week 20); 48 subjects (~11%) had not yet completed Visit 7; and 67 subjects (~16%) had not yet completed Visit 8. These subjects were in United States (n = 16), and other countries (n = 51).

Of these subjects, all had interview-based safety assessments and all but 1 had PEx assessments, with <1% of total without adequate assessment for the primary efficacy outcome because of COVID-19.

The adjustments in this SAP for COVID-19-associated events are listed below and only apply when the event was related to COVID-19. None of the approaches are expected to introduce

bias into the results missing efficacy assessments because COVID-19 is unrelated to treatment assignment.

For events related to COVID-19 only, at Visit 6, Visit 7, and Visit 8 only (FDA COVID-19 Statistical Guidance, June 2020):

- Protocol deviations will be identified as COVID-19 related
- Adverse events will be identified as COVID-19 related
- Concomitant medications given for COVID-19 associated illnesses will be identified as COVID-19 related
- Reduction in dose or interruptions in study product will be identified as COVID-19 related
- Safety laboratory test results done at local laboratories will not be included
- Early or late safety and efficacy assessments that are done out of window due to COVID-19 will be included as observed values
- Last post-baseline observation carried forward will be used for missing data at incomplete visits or missed visits due to COVID-19 only (sensitivity analyses will be performed on observed cases without LOCF imputation) for the following efficacy endpoints:
 - FEV1 % predicted
 - FEV1
 - CFQ-R respiratory symptom domain score for adolescents and adults
 - CRISS score
- No biomarker values and no pharmacokinetic (PK) values will be carried forward

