9.1. Handling of Missing Data

Missing data will not be imputed for efficacy and safety analyses unless specified otherwise. See [Section 4.1.14](#) for handling data during COVID-19 pandemic.

If start or end date of antibiotics is incomplete:

- Missing start day only: If month and year are the same as first dose date of study product, impute the antibiotics start date using first dose date of study product, impute the missing day using '01'
- Missing start day and month, but year not missing: If year is the same as first dose date of study product, impute the antibiotics start date using first dose date of study product. If year is not the same as first dose date, impute the missing day using '01' and the missing month using 'Jan'
- Start date missing completely: impute the missing date using first dose date of study product
- Missing end day only: impute the missing end day using the last day of the month
- Missing end day and month, but year not missing: impute the missing day using '31' and missing month using 'Dec'
- Missing end date completely: impute using last visit date

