9.5. Secondary Efficacy Analyses

The secondary efficacy endpoints ([Section 4.2.2](#)) will be summarized by treatment cohort. Actual values at each visit for each secondary outcome and changes from Baseline will be analyzed. The analyses and summaries of secondary efficacy endpoints will be performed on the mITT population. All secondary analyses will be at or through Visit 8, whichever is relevant, and will be done on observed values only. Two-sided p-values will be presented.

9.5.1. Event Rate per Subject per 28 Weeks of New Pulmonary Exacerbations by Secondary Definition

Analysis of endpoints for various event rates of PEx will be performed using the same method as the primary analysis in [Section 9.4.1](#).

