13. CHANGES FROM PROTOCOL-STATED ANALYSES

- The randomization schedules were initially set up stratified by 1 or 2 versus 3 number of previous PEx requiring IV antibiotics in the previous year as per protocol version 1. Protocol version 3.1 states that the randomization is stratified by 1 versus 2 or 3 number of previous PEx requiring IV antibiotics in the previous year. However, the IWRS was not updated to reflect this change until after 185 subjects had been randomized. Therefore, the number of previous PEx is treated as a continuous variable in the model for the primary and secondary efficacy endpoints.
- The efficacy and safety analyses will generally be based on on-treatment, from start of treatment to end of the treatment period at Week 28. For subjects discontinuing the study early, the treatment period will end at time of discontinuation. The safety follow-up period will be summarized separately for the AEs.
- Additional analyses and methods for handling missing data due to COVID-19 have been incorporated as described in [Section 4.1.14](#), according to recommendations from the FDA COVID-19 related Guidance dated March 2020 and June 2020.
- Additional detail has been added to the SAP regarding the tertiary objectives to facilitate programming and analyses.
- Baseline CFTR-targeting medications use (Yes; No) was added to applicable statistical models.

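### For FEV1 % predicted and CFQ-R values missing because of COVID-19, SAP 4.1.14 makes carry-forward the main handling while 9.5 allows observed values only, so the data tested for hierarchy items 8-11 are not fixed

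*SAP*

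**What the plan says.** SAP section 4.1.14 sets a rule for Visits 6, 7 and 8 only: "Last post-baseline observation carried forward will be used for missing data at incomplete visits or missed visits due to COVID-19 only". The rule covers FEV1 % predicted, FEV1, the CFQ-R respiratory score for adolescents and adults, and CRISS. The same bullet gives the unfilled data a supporting role: "sensitivity analyses will be performed on observed cases without LOCF imputation".

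Section 9.5 governs the secondary endpoints, which include FEV1 % predicted and CFQ-R. It says that all secondary analyses are at or through Visit 8 "and will be done on observed values only". It does not mention COVID-19.

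Two other places bear on which rule prevails:

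- Section 9.1: "Missing data will not be imputed for efficacy and safety analyses unless specified otherwise", followed by a reference to 4.1.14.
- Section 13: "Additional analyses and methods for handling missing data due to COVID-19 have been incorporated as described in" section 4.1.14.

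Section 9.3 sets the fixed testing sequence and 9.5.4 sets the MMRM (treatment, visit, treatment-by-visit, unstructured covariance). Neither names the data set to be tested.

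On timing, section 4.1.2 lists "CFQ-R questionnaire (Visit 1, Visit 5, and Visit 8"), and 4.1.14 says that when restrictions began "all subjects had completed Visit 5 (Week 16) of the study".

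**The concern.** Two programmers could each follow the text and produce different main results for items 8 to 11 (change in CFQ-R respiratory score and in FEV1 % predicted, 20 mg BID then 5 mg BID). These items are in the fixed sequence, so the choice also affects whether later items can be claimed. Section 2 says that the sponsor will not change the SAP after signature except for analyses requested by FDA, so the choice should be settled beforehand.

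The second question is which rule suits a Week 28 estimate. CFQ-R has one scheduled post-baseline score before Visit 8, at Week 16. Carry-forward would therefore normally let a score 12 weeks old stand as Week 28. The planned MMRM can use a subject with a Week 16 score and no Week 28 score without filling anything.

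**Working it through.** **Inputs from section 4.1.14 (status on 16 March 2020).** "18 subjects (~4%) had not yet completed Visit 6 (Week 20); 48 subjects (~11%) had not yet completed Visit 7", and 67 (about 16%) had not completed Visit 8. The target enrolment of 415 is from section 4.1.5.

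**Reproducing the plan's percentages.** 18/415 = 4.3%, 48/415 = 11.6% and 67/415 = 16.1%; by region, 16 + 51 = 67. The stated 11% does not quite fit 415. If percentages are rounded to the nearest whole number, 48/N below 11.5% needs N of at least 418, and 67/N of at least 15.5% needs N of at most 432. The exposed share is then 15.5 to 16.0%. I use 16.1% as the ceiling.

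**Last visit available to carry forward.**

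- 18 subjects lacked Visits 6 to 8: Week 16, a gap of 12 weeks.
- 48 - 18 = 30 lacked Visits 7 and 8: Week 20, a gap of 8 weeks.
- 67 - 48 = 19 lacked Visit 8 only: Week 24, a gap of 4 weeks.

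For CFQ-R the gap is 12 weeks for all 67, unless a later score from a Possible PEx Visit is used.

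**Effect on the Week 28 contrast.** Let m be the filled share, unrelated to outcome, and d16 and d28 the effects at Weeks 16 and 28. For CFQ-R the carry-forward contrast is (1 - m) x d28 + m x d16.

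- Constant effect (d16 = d28): no bias.
- Waning effect, for example d16 = 1.5 x d28, with m = 0.16: 0.84 + 0.16 x 1.5 = 1.08, so inflated by 8%.
- Effect growing linearly from zero to Week 28 (assumed): CFQ-R attenuation is 67/415 x 12/28 = 6.9%. FEV1 % predicted attenuation is (18 x 12 + 30 x 8 + 19 x 4)/(28 x 415) = 532/11,620 = 4.6%.
- Linear growth with 5 to 10% filled instead: 2.1 to 4.3% for CFQ-R and 1.4 to 2.8% for FEV1 % predicted.

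**Error rate and coverage.** These come from simulating the unadjusted Visit 8 CFQ-R difference, with 166 per arm, 16.1% filled at random, correlation between visits of 0.4 and 0.8, and 40,000 runs each. With no effect at either visit, carry-forward rejected in 4.9% of runs. Its empirical SD was 0.109 to 0.110 against a mean nominal SE of 0.110. Coverage of the Week 28 effect was 95.0 to 95.1% (constant effect) and 94.5 to 94.6% (linear growth). For a true effect of 0.30 SD under linear growth, carry-forward averaged 0.279 and the unfilled likelihood estimate 0.300.

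**Price of not filling.** The ratio of CFQ-R interval widths, unfilled to carry-forward, is sqrt((1 - rho^2)/(1 - m) + rho^2). At m = 0.161 this is 1.078 for rho = 0.4 and 1.034 for rho = 0.8; at m = 0.05 it is 1.022 and 1.009. For FEV1 % predicted over seven visits with compound symmetry (assumed), the ratios are 1.065 and 1.023 at the ceiling, and 1.018 and 1.006 at 5%.

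**Power for an assumed CFQ-R effect of 0.30 SD at the ceiling.** The SE with complete data is sqrt(2/166) = 0.110.

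- Carry-forward, constant effect: Phi(0.30/0.110 - 1.96) = 78%.
- Carry-forward, linear growth (0.279 in place of 0.30): 72%.
- Unfilled MMRM, with the SE multiplied by 1.078 or 1.034: 72 to 75% in either case.

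**The case against.** The strongest reply is that the document largely settles the conflict. Section 9.1 allows imputation where it is specified and sends the reader to 4.1.14, and section 13 lists the COVID-19 methods as adopted. Section 4.1.14 itself names the endpoints, visits, trigger and sensitivity analysis. A specific, cross-referenced rule normally prevails over a general sentence. That stands as evidence of intent. It does not remove the word that limits 9.5 to observed values, and that section governs exactly these endpoints without an exception.

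A second reply is that carry-forward does little harm here and can have more power. That also stands: error rate and coverage are sound, and with a constant effect carry-forward gains power. The preference for the MMRM rests on its estimating the Week 28 effect whether or not the effect changes after Week 16.

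A third reply is that the MMRM has its own assumption, and this is right. A reader might infer that the SAP's statement that COVID-19 is unrelated to treatment assignment establishes ignorable missingness. It does not. Table 1 in 4.1.14 includes subjects at high risk in travelling to the site, which may depend on health. Missing at random given the observed data remains an assumption.

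The source of the carried value is a small residue. CFQ-R and spirometry are done at in-person Possible PEx Visits (4.1.3). Section 9 excludes those visits from by-visit analyses unless otherwise specified, and 9.2 counts their assessments when a PEx is confirmed. Section 9.2 can be read as that specification, so the two need not conflict. Still, 4.1.14 does not say whether such a value may be carried forward.

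**Conclusion.** The inconsistency is real, but its severity is minor. The analysis tested for items 8 to 11 has two readings. Carry-forward is the less suitable one for a Week 28 contrast, because its bias depends on how the effect moves after the carried visit: downward if it grows, upward if it wanes, none if it is constant.

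The size rests on an assumed linear growth and on a ceiling. A reader might infer that 16% of Week 28 values are imputed. The SAP does not say so: 67 is the number who had not completed Visit 8 on one date. Visit windows were then widened and out-of-window values kept, so the share finally missing is unknown and probably lower.

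Nor do the documents support reading this as a threat to the main result. The primary endpoint is not filled, and there is no type I error or standard-error problem in the simulated setting. Items 8 to 11 are confirmatory only if the primary and seven earlier secondary tests succeed. Section 3.2's definition of Visit 8 as Visit 8 or study discontinuation is a separate matter: 4.1.14 reports that no subject terminated early because of COVID-19.

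**What to change.** 1. State in 9.5 and 9.5.4 that the MMRM on observed values is the analysis tested in the fixed sequence for items 8 to 11.
2. In 4.1.14, make COVID-19 carry-forward the sensitivity analysis for these endpoints and limit it to values from scheduled visits. Align the reference in 9.1.
3. State that the MMRM assumes data missing at random given the observed data.

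Both analyses are already planned, so their roles swap and the change is to wording. The cost is precision: at the ceiling, intervals are about 3 to 8% wider for CFQ-R and 2 to 7% for FEV1 % predicted, with some power lost if the effect is constant. If the sponsor prefers carry-forward as the main analysis, 9.5 still needs an explicit exception and 4.1.14 a definition of the value carried.

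Separately, 9.5.4 names a two-sample t-test and a rank-sum test for change from baseline within the same group. These compare independent groups. Replace them with the paired t-test and the signed-rank test.
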